# 14.0 Comparison of usual care and study procedures

14.1 Describe the current alternatives to participation in this research study. For example, alternative treatments or alternative care the participant could receive outside of the study.
Describe factors that influence which treatments a participant receives.

CJC-TraC activities are optional and intended to supplement, not replace, existing WIDOC activities that help coordinate release planning.

WIDOC Social Workers use the list created of all releases happening within the next 6 months and use that to start the release process with individuals. This process includes a working document to make sure people are set with living arrangements and other priorities before leaving the facility. All people will receive the same standard of care even if they choose not to enroll in the study. Study participants will get the additional support pre- and post- release, in a way that is coordinated and not duplicative of what is being done.

14.2 Describe standard practice or standard of care for this participant population at the UW-Madison/UW Health. For example, a certain treatment or follow-up schedule that is recommended.

Patients with HIV who receive care at UW Health will receive case management from the UW HIV Clinic prior to release and those people who choose to enroll in CJC-TraC will be coordinated with this in a patient centered way, to reinforce any other care plans or referrals rather than replace or duplicate.

14.3 List any research procedures that overlap with standard practice or standard of care at UW-Madison/UW Health. For example, does study follow-up occur at the same timepoints as standard of care follow-up? Would the same screening or follow-up assessments be done as part of standard care?

As stated above, CJC-TraC will be used to reinforce the care plan that is made as part of routine procedures, educate about its importance, and supplement case management activities that address needs still unmet.

14.4 Describe whether / how research participation would affect standard clinical care (e.g., require participants to delay or withhold standard clinical treatment for x period, substitute the most common Rx with an investigational treatment, etc.). Describe how the study will minimize risks associated with delaying or withholding clinical alternatives.

Participation in the study would not affect standard clinical care of the participant. If a participant has care arranged after release from prison (e.g. pre-scheduled provider visits or activities completed by a different case manager), the Nurse Case Manager will integrate the established care into the participant plan.

# 15.0 Withdrawal of Participants

15.1 Describe anticipated circumstances under which participants will be withdrawn from the research without their consent.

**Primary Objective (feasibility and acceptability):** Participants will be withdrawn if they're exhibiting ongoing aggressive, harassing, or threatening behavior. Participants will be evaluated individually by the Nurse Case Manager and research staff, and the subject may be removed from study if we feel it is in the best interest of the subject, staff, and other study participants.

Participants will also be removed from the study if they have an extension to their sentence and they are no longer within 3 months of release. They will be eligible to re-enroll in the study if their release date falls within 3 months while the study is ongoing.

Page 26 of 37 Revised: February 16, 2023

The Nurse Case Manager will attempt to reach the participant 4 times after release. On the 5th unsuccessful contact attempt, the participant will be considered lost to follow up and the nurse case manager will cease attempts to contact. The Nurse Case Manager will fill out the Post-Release Contact Log to keep track of these attempts. [See Contact Log] If the participant has a cell phone provided by the study, the cell phone's plan may be terminated at this point. A study team member will attempt to contact the participant through various means to complete the End-of-Study Assessment.

**Secondary Objective (preliminary assessment of effectiveness):** Not applicable. Preliminary assessments for effectiveness only involves secondary data analysis using administrative data. This objective does not require any in-person encounters with participants or site visits to either WIDOC facility in the study.

# 15.2 Describe any procedures for orderly termination.

Participants who are terminated early from the study will be notified by the Nurse Case Manager. After termination, no additional data will be collected directly from participants the context of the intervention. Population-level data for the secondary objective will continue to be collected. Data previously collected to that point will be used in analyses as appropriate.

# 15.3 Describe procedures that will be followed when participants withdraw from the research, including partial withdrawal from procedures with continued data collection.

**Primary Objective:** If participants wish to withdraw from the study, they can do so at any time by contacting the Nurse Case Manager or any of the study contacts listed in the consent form. If a participant indicates they wish to withdraw, they will not be asked to complete the 3 month survey or exit interview as detailed above. If a participant indicates that they do not wish to participate in any aspect of the intervention (i.e. phone calls with the case manager after release), they will be allowed to decline. They will be asked if they would agree to participate in the 3 month survey and potentially the exit interview. They will receive the same compensation as participants who completed all aspects of the study. Both the 3 month survey and the option for an exit interview are documented in the consent form.

Any meetings or appointments with health care providers or others that have already been scheduled will remain in place in the event of a participant's premature withdrawal from the study.

**Secondary Objective:** Not applicable. Preliminary assessments for effectiveness only involves secondary data analysis using administrative data. This objective does not require any in-person encounters with participants or site visits to either WIDOC facility in the study.

# 16.0 Data Management and Confidentiality

- 16.1 Describe any procedures that will be used for quality control of collected data.
- 16.2 Describe the steps the researchers will take to secure the data (e.g., training, authorization of access, password protection, encryption, physical controls, certificates of confidentiality, and separation of identifiers and data) during storage, use, and transmission. If HIPAA rules apply to the study, review information on the Office of Compliance HIPAA page and consult HIPAA Privacy and Security Coordinators to ensure that data management methods are compliant. Select all that apply:
  - X Data will be coded, and the "key" linking identities to codes will be kept separately from the data.
  - □ Data will be coded, and the "key" linking identities to codes will be kept on paper only. The study data will be stored electronically and labeled only with codes.

hepatitis C and substance use disorder ☐ Only those listed as key personnel will have access to the "key." ☐ Access to the "key" will be limited to the following person (e.g., Database Administrator): \_\_ X This study is funded by the National Institutes of Health and is covered by a Certificate of Confidentiality. ☐ This study is NOT funded by the National Institutes of Health but because it will collect sensitive information, the research team will apply for a Certificate of Confidentiality to protect data from being requested without the subject's consent as part of a legal proceeding. □ Other: \_\_\_\_\_\_ 16.3 Describe how and where data and/or specimens will be stored and maintained. The following list is provided for convenience but is not an exhaustive list. Select all that apply: ☐ Online Collaborative Research Environment (OnCore) Biospecimen Management X Research Electronic Data Capture (REDCap) Specify which instance you will be using (e.g., ICTR's, Department of Medicine's): DOM REDCap ☐ Other software option that will be stored on departmental server. Specify the department: X Locked filing cabinet or drawer inside a locked room. Specify the building: ☐ Other (describe): \_\_\_\_\_ **X** Data will not be stored or accessed on portable devices. ☐ Portable devices will be used to access secure web-based data collection sites such as ICTR's REDCap. No data will be stored locally on the device. X Data stored on portable devices will be coded with the key stored separately. No identifiers will be stored on portable devices. ☐ Data stored on portable devices and therefore only encrypted devices will be used. 16.4 Management of Identifiers: Explain whether there will be a unique code on the specimen/dataset that can be used to LINK to a participant's identity, but will not, by itself, reveal who the participant is. If you will create and maintain a "key" linking identities to codes, explain where this key will be stored. Define when identifiers (such as names) or the "key" linking codes to identifiers will be destroyed, if known. Please modify the common options below as needed. ☐ Identifiers will be destroyed after all data has been collected. X Identifiers will be destroyed at study closure. ☐ Identifiers will be destroyed at study closure or at the time of publication.

PROTOCOL TITLE: Health systems innovations for supporting transitions of care for incarcerated people living with HIV,

**Primary Objective:** For purposes of the study, participants will be labeled with a unique identifier. The key linking the participant to their identifier will be stored on a password protected, encrypted computer and will be saved separately from the participant information.

Hard copies or printed materials that are saved will be stored in a locked cabinet in within the DOC until it can be transferred and stored at UW Medical Foundation Centennial Building (MFCB) in a locked cabinet with all CJC-TraC Study documents. Paper documents (e.g. notes written by the NCM, Health Service Requests, Interview Request Forms) may be scanned into an electronic file and then destroyed. The participant key will be destroyed upon closure of the study.

**Secondary Objective:** Identifiers associated with the Medicaid enrollment system are maintained as part of a large integrated data set at IRP through omnibus data sharing arrangements in the support of multiple UW projects. The destruction of these identifiers will comply with terms of agreements between IRP/UW and the WI Department of Health Services Identifiers from the WI Department of Corrections, the WI Department of Public Health, and the WI State Lab of Hygiene will be retained on the restricted IRP server only until analyses are complete and the findings have been presented and/or published. IRP will comply with each agency's data destruction terms in the respective data use agreements.

- 16.5 Describe any planned sharing of data and/or specimens outside the study team / institution. Include sharing required by funding agencies and publications.
  - What data and/or specimens will be shared.
  - Whether data/specimens will have all identifiers (including linking codes) removed prior to sharing, or if they will remain linked to participant identifiers.
  - How data and/or specimens will be transmitted or transported.
  - If the study will share large-scale genomic data under the NIH Genomic Data Sharing Policy, review HRP-064, SOP NIH GDS Institutional Certification and HRP-332 Worksheet NIH GDS Institutional Certification to ensure that you provide adequate information for institutional certification.

**Primary and Secondary Objectives:** All data access will be done by people who are part of the study team. No data will be shared outside the study team.

# 17.0 Provisions to Protect the Privacy Interests of Participants

17.1 Describe the steps that will be taken to protect participants' privacy interests. "Privacy interest" refers to a person's desire to place limits on with whom they interact or to whom they provide personal information. If any of the following apply, check the box for convenience:

**Primary Objective:** Procedures will be performed in a private area where others (e.g. prison staff) will overhear the conversation between participant and the Nurse Case Manager. All members of the study team are up to date on their institutional HIPAA training, as well as CITI training. The study is not collecting information that could pose legal or reputational risks to participants.

**Secondary Objective:** As stated in the Phase 1 IRB application (2020-0749), collection of sensitive information about subjects is limited to the amount necessary to achieve the aims of the research.

17.2 If the study collects sensitive information (e.g., sexual health information, communicable disease status, genetic test results), provide a justification for this.

Due to the goal of connecting people with health care services after release from prison, the study will collect information related to HIV status, HCV status, and substance use history. These data will be collected firstly for the purpose of eligibility, but also for more complete post release care planning by the Nurse Case Manager.

17.3 Describe what steps you will take to make the participants feel at ease with the research situation in terms of the questions being asked and the procedures being performed. "At ease" does not refer to physical discomfort, but the sense of intrusiveness a participant might experience in response to questions, examinations, and procedures.

Page 29 of 37 Revised: February 16, 2023

**Primary Objective:** Our research team has previous experience working respectfully and sensitively with vulnerable populations in research settings and have learned additional strategies for building rapport and trust with incarcerated individuals through the qualitative interviews conducted in Phase I of this study.

The Nurse Case Manager is taking a patient-centered approach. This means that the meetings with the participants and the peripheral duties performed (e.g., finding additional resources, making referrals) will be tailored to the specific needs of the patient/participant. In the interviews performed in Phase 1 we learned that oftentimes after release individuals feel overwhelmed by all that they need to accomplish and by the variety of concerns that they carry with them. By addressing concerns that are raised beyond accessing primary care after release, the Nurse Case Manager will help the participant feel more in control, decreasing feelings of discomfort.

Lastly, participants can take breaks as needed or choose not to complete any study activity that causes undue stress or discomfort.

**Secondary Objective:** Preliminary assessments for effectiveness only involves secondary data analysis using administrative data. This objective does not require any in-person encounters with participants or site visits to either WIDOC facility in the study.

17.4 If any medical records from UW Health or other sources will be used, confirm that the study team has authorized access to the records and that this use is allowed by the legal medical record holder.

**Primary and Secondary Objectives:** No medical records from UW Health will be accessed as part of the study. The Wisconsin Department of Corrections will grant EMR access to the Nurse Case Manager, so they are able to gather information needed to determine eligibility and to see a more complete clinical picture of the participant.

# 18.0 Sharing of Results

18.1 Describe whether results (study results or individual participant results, such as results of investigational diagnostic tests, psychological assessments, genetic tests, or incidental findings) will be shared with participants or others (e.g., the participant's primary care physicians) and if so, describe how the results will be shared. Specify whether individual results will be reported in participants' health records.

Data obtained from participants through research assessments and surveys will not be shared outside the study team. There will be no diagnostic assessments done as part of research activities. The Nurse Case Manager may document information relevant to the transitional care plan or nursing assessments or interventions (including referrals to medical providers) in the EMR.

18.2 Describe plans to share study results with the public.

Results from the study will be deidentified prior to any publications or presentations. It is anticipated that upon study completion manuscripts will be prepared for publication. Presentations at the National Commission for Correctional Health Care and the Academic Consortium for Criminal Justice Health conferences will be possible venues for sharing findings of the study.

# 19.0 Data and Specimen Banking

19.1 If data and/or specimens will be banked for future use, indicate whether banking is optional. Describe what data/specimens will be banked, where they will be stored, how long they will be stored, how the data/specimens will be accessed, and who will have access to the data/specimens. Describe any procedures that will be used for quality control of collected data and specimens.

Page 30 of 37 Revised: February 16, 2023

**Primary Objective:** No specimens will be used in this study. Data collected from participants (e.g. survey responses) will be removed of identifiers prior to banking at the completion of all study activities. No identifying participant data will be banked. Banking the participant data is not optional in this study. Banked data will be kept indefinitely for future use. Data will be banked to assist in future analyses to improve implementation at future sites. All banked data will be stored on an encrypted, password protected server accessible only to the research team.

Multiple de-identified databases (e.g. survey data and Medicaid outcomes) will contain a unique code number that is linked to identifying information in a separate master list that matches participant identifiers to their unique research code. This linking database is only accessible to research staff and will be destroyed after data analysis has concluded. Banked data will include a unique code, but will not include direct identifiers including name and date of birth.

**Secondary Objective:** Not applicable. There will be no data banking as part of the secondary objective.

19.2 List the data to be stored and/or the data associated with each specimen. Specify whether data/specimens will have all identifiers (including linking codes) removed prior to banking, or if they will remain linked to participant identifiers.

The data from the baseline and follow up assessments. All banked data will be stored on an encrypted, password protected server accessible only to the research team with no identifying participant data.

19.3 Describe the procedures to release data or specimens, including: the process to request a release, approvals required for release, who can obtain data or specimens, and the data to be provided with specimens. Describe any limits on future research use of the banked data/specimens.

The PI of the study, [name], will review all requests to release banked data. The banked data will only be accessible to the research team unless a written request is approved by the study PI.

19.4 State whether participants may withdraw their banked data/specimens from future research use. If yes, explain whether data/specimens would be destroyed or fully anonymized in response to a withdrawal request. If no, explain why (e.g. data/specimens are fully anonymized prior to banking).

All banked data will be fully anonymized prior to banking.

# 20.0 Study Analysis

20.1 Statistical Hypotheses: State the formal and testable null and alternative hypotheses for primary and key secondary endpoints, specifying the type of comparison (e.g., superiority, equivalence or non-inferiority, dose response) and time period for which each endpoint will be analyzed.

**Primary Objective:** The main hypothesis to be tested in this pilot study is that the CJC-TraC protocol is feasible and acceptable to WIDOC staff and incarcerated patients.

**Secondary Objective:** The secondary objective is descriptive and not hypothesis driven. The objective is to describe secular trends in health care use among the population from which CJC-TraC participants were recruited. These trends provide a counterfactual regarding what we observe in the absence of the intervention.

Page 31 of 37 Revised: February 16, 2023

20.2 Sample Size Justification: Include number of participants to recruit, screen, and enroll to have adequate power to test the key hypotheses for the study. Include anticipated impact of dropout/withdrawal/cross-over rates, missing data, etc. on study power. Provide all information needed to validate your calculations.

The proposed sample size was chosen by considering what would be an appropriate case load and frequency of client interactions for the Nurse Case Manager. This level was informed by focus group data collected in Phase 1 and input from collaborators, and eligible participants at the two correctional institutions where the study will occur. Publicly available data from the Department of Corrections indicates that Oakhill Correctional has approximately 316 annual releases while Robert E. Ellsworth Correctional Center (REECC), a facility in the Wisconsin Women's Correctional System (WWCS), has approximately 327, for a total of 643 annual releases at the two study sites. There are 112 and 65 people released to Dane and Milwaukee counties annually at Oakhill and REECC respectively, for a total of 177. These counties will be prioritized for recruitment. An additional 126 individuals released annually to Rock, Waukesha, Racine, and Kenosha counties, 62 from Oakhill and 64 from REECC. These counties can be adequately serviced by the NCM at this time, and the number of serviceable counties will increase throughout the intervention. Assuming that 50% of people incarcerated at the two facilities and releasing to a serviceable county will be eligible and enroll in the study, we would expect a total of 168 participants at Oakhill Correctional Institution and 120 at REECC over the 24-month study period, for a total of 288 total participants. Our recruitment goal is 220 individuals.

20.3 Participant Population(s) for Analysis: Identify and describe the analysis datasets (e.g., which participants/populations will be included in each).

The dataset construction begins with all individuals released from a WI state correctional facility between 1/2020-12/2023. From this universe of individuals, we will apply the sample criteria noted in 5.4 to generate the analytic dataset: adults who have a history of, or living with, SUD, HCV or HIV and enroll in Medicaid within the month of release.

20.4 Statistical Methods: Summarize the overall statistical approach to the analysis of the study data.

We will implement descriptive analyses to achieve the following objectives: a) to characterize and compare the equivalence of sample characteristics and outcomes across study years; b) to describe, and test for change over time in unadjusted study outcomes; and c) to quantify the association between study outcomes and factors that may influence those outcomes including beneficiary characteristics. We will use bivariate statistical tests (e.g., t-test, chi-square test) to determine the equivalence of unadjusted characteristics and outcomes over time, and regression methods to estimate changes over time in study outcomes, controlling for individual and areas-level characteristics. For binary outcomes, we will implement logistic regression. For count outcomes, we will implement Poisson regression.

20.5 Planned Interim Analysis: Interim efficacy or safety analyses if planned, and include a description for stopping rules for efficacy and stopping rules for safety.

Interim analyses for feasibility and fidelity will be conducted aligned with the Replicating Effective Programs, such as logging the intensity and frequency of time spent by the Nurse Case Manager on participants, as well as analyses to identify statistically significant barriers to accessing care after release.

20.6 Handling of Missing Data: Describe how missing data will be handled, e.g., type of imputation technique, if any, and provide justification. (Most methods for handling missing data assume that the data are missing at random, which may not be a valid assumption.) WIDOCument reasons for missing data and evaluate the impact of missing data using sensitivity analysis. (If

Page 32 of 37 Revised: February 16, 2023

the missing data are extensive, model-based approaches will estimate their effects under various assumptions regarding missingness.)

Missing data will be considered based on the extent and intensity of the missingness. Steps have been implemented to reduce missingness such as researcher administered surveys, and so we anticipate that missing data will occur randomly. If missing data is extensive, approaches to mitigate the effect of the missing data will be used to generate a functional final model.

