# State the hypotheses to be tested.

The main hypothesis to be tested in this pilot study is that the CJC-TraC protocol developed in collaboration with WIDOC partners will be successfully implemented in a way that is deemed acceptable to WIDOC staff and incarcerated patients. We will consider implementation to be successful if (1) we enroll a substantial number of eligible participants (e.g. at least 50% of the targeted sample size of 220), and (2) Participants complete post-incarceration study activities with a reasonable rate of retention (e.g. fewer than 50% of participants being lost to follow-up after

release). We will assess acceptability by systematically querying study participants and WIDOC staff about their experience with CJC-TraC using validated questionnaires, as described below.

A secondary hypothesis is that individuals who participate in the CJC-TraC pilot will have a higher rate of using non-emergency, outpatient health services (e.g. primary care clinic appointment) after incarceration, in comparison to contemporaneous rates of health service utilization by individuals with comparable levels of comorbidities and demographic characteristics.

2.2 Define the primary and secondary study endpoints. A study endpoint is a specific measurement or observation to assess the effect of the study variable (study intervention). Study endpoints should be prioritized and should correspond to the study objectives and hypotheses being tested.

In this pilot study we will assess endpoints related to feasibility, acceptability, and effectiveness, as described above:

Primary Endpoints: Feasibility

- The number of participants who are enrolled and complete the baseline study assessment per month, at each of two institutions;
- The number of pre-release CJC-TraC intervention sessions completed with the nurse case manager for each participant, at each institution;
- The number of post-release telephone contacts between the CJC-TraC nurse case manager and study participants;
- The proportion of study participants who are retained in follow-up for three months and complete the end-of-study assessment.

Primary Endpoints: Acceptability

- The proportion of study participants who rated specific aspects of the intervention useful and encounter volumes appropriate, collected on 3 month survey.
- The subjective experience in the program regarding prison-to-community transition support and healthcare support, collected by participant interview.

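### Section 2.1 states a directional comparison with contemporaneous, comparable people, but Section 20 calls the secondary objective descriptive and specifies no adjusted participant-versus-comparator estimate; the trend used as counterfactual is not like for like.

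*Combined protocol and SAP*

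**What the plan says.** Section 2.1 gives the secondary hypothesis a direction and a comparator: "individuals who participate in the CJC-TraC pilot will have a higher rate of using non-emergency, outpatient health services", "in comparison to contemporaneous rates of health service utilization by individuals with comparable levels of comorbidities and demographic characteristics". Section 2.2 lists two effectiveness endpoints: the count of non-emergency outpatient visits in the 3 months after release, and the days from release to the first such visit.

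Section 20.1 says "The secondary objective is descriptive and not hypothesis driven", and adds of the population trends: "These trends provide a counterfactual regarding what we observe in the absence of the intervention". Section 20.3 defines one dataset: "The dataset construction begins with all individuals released from a WI state correctional facility between 1/2020-12/2023", narrowed by the Section 5.4 rules. Section 20.4 plans "regression methods to estimate changes over time in study outcomes, controlling for individual and areas-level characteristics", and aims "to quantify the association between study outcomes and factors that may influence those outcomes including beneficiary characteristics". On models it says: "For binary outcomes, we will implement logistic regression. For count outcomes, we will implement Poisson regression". The t-test and chi-square test are given as examples for unadjusted comparisons across years.

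Participants enter only in Section 13.1. There, signs of effectiveness are to be judged by how far participants' health care use departs from the population trend, and the trend stands for people who could plausibly have had the program but did not get it.

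**The concern.** The plan makes a between-group claim in one section, disowns it in another, and analyses something else. Section 20 asks whether outpatient use changed over calendar time in the released population. Section 2.1 asks whether participants used more care than similar people released at the same time. The first does not answer the second.

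The gap would matter little if the trends were offered only as background, but they are called a counterfactual in Sections 13.1 and 20.1. Section 2.1 also says that the preliminary effectiveness data will be used to plan later studies that formally test effectiveness and cost-effectiveness. An unadjusted departure from a reference that differs in site, sex mix, entry rules and period could be carried forward as a program effect when it partly reflects who was enrolled.

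**Working it through.** **Hypothesis against analysis**

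| Element | Section 2.1 needs | Sections 20.3–20.4 give |
|---|---|---|
| Groups | Participants and comparable others | One statewide cohort; no participant set or participation variable named |
| Contrast | Participants minus comparators | Later years against earlier years |
| Adjustment | Comorbidity and demographics | Individual and area characteristics, attached to the time trend |
| Timing | Contemporaneous | Releases 1/2020–12/2023 |

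**Is the reference like for like?**

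- *Cohort size.* Section 4.0 gives about 9,000 releases a year and 70% with a qualifying condition. Over four years, 9,000 × 0.70 × 4 = 25,200. The plan states about 20,000 (20,000 / 25,200 = 0.79) without explaining the difference; the Medicaid rule in 5.4 may account for it. I use 20,000 below.
- *Sites.* Section 4.0: 316 + 327 = 643 releases a year at the two sites; 643 / 9,000 = 7.1%. The pilot also gives priority to releases to Dane and Milwaukee counties.
- *Sex mix.* Section 3.0 sets the pilot at about equal numbers of men and women. The cohort takes whatever mix the state releases, which the documents do not give. Section 1.2 reports that women are more likely than men to have an outpatient visit within 30 days, so a difference in mix alone can move the contrast.
- *Entry rules (5.4).* Substance use disorder is self-reported for participants but is a COMPAS-identified need for the cohort. Participants must be eligible for Medicaid and willing to enroll before release; the cohort must be enrolled within one month of release.
- *Volunteering.* Section 4.0 expects about 70% of eligible people to agree, so about 30% decline. The cohort has no such selection.
- *Period.* January 2020 to December 2023 is 48 months. Phase 2 starts in March 2022 (Section 12.0), so the overlap is 10 + 12 = 22 months; 22 / 48 = 46%.
- *Participants in the comparator.* Section 13.1 describes people who did not get the program, but Section 5.5 adds no exclusions. At full enrollment the overlap is at most 220 / 20,000 = 1.1%. In a 22-month cohort, if releases are even, 20,000 × 22/48 = 9,167 and 220 / 9,167 = 2.4%. Both are upper bounds, since some participants may not meet the cohort's rules. The dilution is negligible.

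**Endpoints against methods**

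Poisson regression fits the visit count. For days to first visit, a t-test or Poisson model needs a number of days for everyone. People with no visit have none, and Section 23.1 expects some re-incarceration within the 3 months. No named method deals with either.

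**Precision of a direct comparison (illustration on assumptions outside the plan)**

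Take a binary 30-day visit, 34% in both groups (the background rate in Section 1.2), 220 participants, 20,000 comparators and no confounding. The 95% half-width is 1.96 × √(0.34 × 0.66/220 + 0.34 × 0.66/20,000) = 0.063, about 6 percentage points. With 110 participants it is about 9 points. This is usable as preliminary evidence, if reported with its interval.

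**The case against.** The best defence is that most of the protocol treats the aim as descriptive. The Study Summary speaks of preliminary evidence, Section 4.0 of a descriptive analysis of concurrent trends, and Section 2.1 leaves formal testing to later studies and calls only the main hypothesis one to be tested. On that view the secondary hypothesis is a stray sentence. A descriptive secondary aim is indeed acceptable in a single-group pilot sized on case load.

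Several stronger readings are tempting and are not supported:

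- *That the plan compares participants with nobody.* Section 13.1 commits to an informal comparison. What is missing is a specified, adjusted estimate with an interval.
- *That days to first visit has no method at all.* It is worded as a number of days, so the t-test or Poisson model could be meant. The sound criticism is that neither handles people with no visit.
- *That participants in the cohort contaminate the comparator.* The definition is inconsistent, but about 1% is negligible.
- *That the years before March 2022 should not be there.* They are legitimate for describing trends and mislead only if read as contemporaneous.
- *That the data cannot identify participants.* The appendix of data elements is not in the text available, so the absence of a participant flag cannot be inferred.

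The Section 20.4 covariates and its analysis of factors could be extended to participation, but the text does not do so. The conflict between 2.1 and 20.1 and the unadjusted, non-comparable reference therefore remain.

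**Conclusion.** The point holds as a specification gap in the secondary aim, and it should be corrected before analysis. Neither of the two secondary endpoints has a specified adjusted participant-versus-comparator estimate. The informal comparison uses a reference that differs in site, entry rules and period, and whose sex mix is not aligned with the pilot's. The wording conflict and the missing estimate rest on the text alone. The counts rest on the plan's own figures: 7% of releases from the two sites, 22 of 48 months in Phase 2, and an overlap of at most about 1%.

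A reader might infer that the comparison will favor the program. The documents do not establish the direction or size of any net bias: they give no statewide sex mix, no outcome rates by site and no comparison of volunteers with decliners. The primary feasibility and acceptability conclusions do not depend on this comparison.

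**What to change.** Reconcile Sections 2.1 and 20.1 in one of two ways.

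**Preferred.** In 20.3–20.4, compare participants with non-participants released in the same period and remove participants from the comparator. If any participant is released after December 2023, extend the window or state that they are left out. For each secondary endpoint, report a difference with a 95% confidence interval, adjusted at least for sex, age, race, county, qualifying condition and release period. Use a count model for visits and a time-to-event method for days to first visit, stating how people with no visit and re-incarceration are handled. Label the result preliminary and non-causal, and name volunteer selection as residual confounding. Entry rules can be aligned in a sensitivity analysis, with a caution: help with Medicaid enrollment is part of the intervention (Section 11.1), so conditioning on enrollment may remove part of the program's effect.

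**Minimal.** Reword the secondary hypothesis in 2.1 as an expectation, drop the counterfactual wording in 13.1 and 20.1, and show participants' outcomes descriptively beside same-period trends stratified by sex. The Study Summary objective, the 2.2 endpoints and the consent-waiver rationale in 6.1 can then stay.

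**Cost.** The preferred option needs SAP wording, one model per endpoint and a participant-status link to the population file. Participants' Medicaid data are already collected for a year after release (Section 12.1) and coded to a master list (Section 19.1). The visible text does not confirm a link to the population file, where investigators see masked identifiers (Section 8.1), so this should be checked first. The minimal option is mainly wording plus a stratified display. Residual confounding remains under either.
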